6.4 Subject Disposition and Analysis Populations

No formal analysis population is defined. All available data on treated subjects will be included in the efficacy and/or safety analysis of the data. A disposition table for CT-AMT-061-01 for all subjects will be provided. Summary tables with information regarding protocol deviations and withdrawal reasons (reasons for subject withdrawal from the study) will also be provided.

The data on subject disposition and informed consent will be listed.

6.5 Demographic and Baseline Characteristics

Descriptive summaries of demographic and baseline characteristics will be presented. The following descriptive statistics will be included: number of observations, mean, standard deviation, median, minimum and maximum for quantitative data. For qualitative data, frequency counts and percentage will be determined.

Other baseline data including: Medical History and Concomitant Illnesses, Prior and Concomitant Medication/Therapy, Hemophilia B Status and History, History of Bleeding and FIX use, blood pressure, pulse, body temperature, physical examination results, height, and weight will be presented in listings. Gene sequencing results (FIX gene mutation) will be listed.

Medical history will be coded using the most recent version of the Medical Dictionary for Regulatory Activities (MedDRA) and listed for each subject

6.6 Investigational Product Exposure

Listings for exposure to investigational product will be presented.

6.7 Efficacy Analyses

All efficacy analyses will be performed for all treated subjects. All presentations will be done on an individual level or by using descriptive statistics. Plots and tabular displays will be created, visualizing individual effects for the selected efficacy measures as specified in the following sections.

6.7.1 Primary Efficacy Endpoint

The primary efficacy endpoint is the FIX activity level at Week 6 post dose. If FIX replacement therapy was used within 10 days of the Week 6 post-dose time point, the Week 8 post-dose FIX activity level will be used. If FIX activity is still contaminated, then the Week 10 post-dose FIX activity level will be used, etc. This would result in a corresponding postponement of the nominally Week-6 interim efficacy analysis.

FIX activity levels will be presented in % of normal units. Descriptive statistics (across visits) including the mean, standard deviation, median, minimum, and maximum will be presented at six weeks after dosing by subject. Such descriptive statistics will also be displayed by visit across subjects.

The Week 6 primary analysis of FIX Activity will proceed as follows. FIX activity will be summarized (and listed) by visit over the 6-week period since administration of AMT-061. By-subject plots of FIX activity over time will be overlaid with plots of exogenous FIX consumption (start and end times) and with the times of occurrence of bleeding events over the first 6 weeks subsequent to AMT-061 administration.

Plots of FIX activity levels over time per subject will be presented. Descriptive statistics and plots will display uncontaminated results only, i.e. FIX activity levels that are not affected by exogenous FIX use during the trial. Alternatively, the by-subject FIX activity plots may display the time of exogenous FIX use instead of altogether omitting the contaminated FIX results. The required wash out period (in order to consider a FIX activity level to be “unaffected” – i.e. “uncontaminated”) will be 10 days. FIX activity level over six weeks after dosing (by subject) will also be listed and will include a flag for contaminated results. These analyses will be presented in the Week 6 iCSR.

The above-mentioned set of analyses – being done for the Week 6 CSR will also be carried out for the Week 52 main CSR (and 2.5 Years CSR), but over the time period of 52 Weeks (and 2.5 Years) instead of over 6 weeks.

For the Week 6 and 52-Week data-cut analyses, the contamination rule, as stated above, was 10 (discrete) days. Specifically - Factor IX activity levels during the period of use or within 10 days after the end of use of exogenous factor IX replacement therapy were not included in these analyses; the last (calendar) day of use and the subsequent nine (calendar) days are considered to be contaminated. Beginning with the 2.5-year (data cut) analysis, the contamination rule is hereby refined as follows. Factor IX assessments post-AMT-061 that are within 5 half-lives of exogenous factor IX use are considered contaminated and will be excluded from the analysis. Going forward, this 5-half-life contamination rule replaces the 10-day contamination rule. Both the date and time of the exogenous factor IX infusion start and the blood sampling for factor IX activity assessment will be taken into account to determine whether there was contamination. If the factor IX activity assessment was performed prior to the infusion start time, then the assessment is not considered to be contaminated by that infusion. See further detail in the [Data Handling Rules Appendix](#) in this document [under the category of “Contamination due to exogenous factor IX (infusion) use”].

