3 TRIAL DESIGN

3.1 Overall Trial Design

This is a Phase IIb, open-label, single-dose, single-arm, multi-center trial consisting of a screening, a treatment plus post-treatment follow-up, and a long-term follow-up phase.

After a screening period of maximal six weeks, eligible subjects will receive a single IV dose of 2×10^{13} gc/kg AMT-061 and will thereafter be followed for a total of five years (60 months). Post-treatment follow-up visits are planned as follows:

- Weekly up to Week 12
- Every 2nd week from Week 12 to Week 26
- Every month from Week 26 to Week 52

All subjects will continue to be followed every half year from Week 52 to 60 months (4 years long-term follow-up).

The subjects will be monitored for tolerance to the IMP and detection of immediate AEs for 24 hours (overnight stay) after dosing. The dosing of the subjects must be separated by a minimum of 14 calendar days to allow for subject safety monitoring and to ensure appropriate action can be taken in case any acute reactions are observed.

One interim analysis will be performed after six weeks post-dose to determine the efficacy of AMT-061 in terms of factor IX activity.

After 52 weeks post-dose and 2.5 years post-dose, efficacy and safety data will be collected on all subjects. These data will be locked, analyzed, and reported in a CSR (52-week analysis) and CSR addendum (2.5-year analysis). Data from that point will be considered locked and will not be changed. At the end of the 4-year long-term follow-up period (60 months/5 years post-dose), all safety and efficacy data will be reported in a CSR addendum covering the entire study period including the final 2.5 years post-dose follow-up period (5-year analysis).

The end of the clinical trial is defined as the point in time when the last subject has completed the overall follow-up observation period of 5 years after administration of the IMP.

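### The Week 6 fallback in SAP 6.7.1 is tied neither to the actual sample nor to the SAP's own contamination rule, so the two can disagree about the primary value

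*SAP*

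**What the plan says.** The primary endpoint is factor IX activity at Week 6. SAP 6.7.1 adds a fallback: "If FIX replacement therapy was used within 10 days of the Week 6 post-dose time point, the Week 8 post-dose FIX activity level" is taken instead. It goes on: "If FIX activity is still contaminated, then the Week 10 post-dose FIX activity level will be used, etc". The interim analysis is then postponed to match.

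The same section defines contamination. For the Week 6 and Week 52 data cuts, "Factor IX activity levels during the period of use or within 10 days after the end of use of exogenous factor IX replacement therapy" were left out, and the count is spelled out: "the last (calendar) day of use and the subsequent nine (calendar) days are considered to be contaminated". The definition then changes: "Beginning with the 2.5-year (data cut) analysis, the contamination rule is hereby refined as follows". From that cut the criterion is 5 half-lives, judged by date and time, and "If the factor IX activity assessment was performed prior to the infusion start time, then the assessment is not considered to be contaminated by that" later infusion.

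Protocol 3.1 schedules visits "Weekly up to Week 12". Protocol Table 2 has central factor IX activity at each of these visits, with a window of plus or minus 2 days (repeated in SAP Table 3). Protocol 9.9.1 gives the 10-day wash-out but no Week 8 or Week 10 fallback.

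**The concern.** Two tests in one section decide whether a Week 6 value can stand as primary, and they are built differently. The fallback measures distance from the nominal Week 6 date and gives no direction. The contamination rule measures forward from the last infusion to the sample. When they disagree, there are two possible errors. A valid, on-time value may be replaced by one taken weeks later. Or a contaminated value may be excluded without the fallback supplying another. In the second case SAP 6.3 offers little help, because only unplanned assessments may fill a missing scheduled value.

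The primary endpoint is described in three planned subjects. Under Section 9 of the DMC Charter, the 6-week data inform the recommendation on the Phase 3 dose. The contamination flag in the listing could also contradict the value labelled primary.

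**Working it through.** The plan gives no figure to reproduce here, so the check is a count of calendar days.

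**Inputs.** Days are counted from dosing, so Weeks 6, 7, 8 and 10 are Days 42, 49, 56 and 70. The Week 6 sample day *s* may be 40 to 44 (window of plus or minus 2 days). A single infusion falls on Day *u*.

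**Rules.**
- Contaminated (SAP 6.7.1, 10-day rule): 0 ≤ *s* − *u* ≤ 9, i.e. *u* from *s* − 9 to *s*.
- Fallback, literal reading: |*u* − 42| ≤ 10, i.e. *u* = 32 to 52 (21 days).
- Fallback, earlier use only: 0 ≤ 42 − *u* ≤ 10, i.e. *u* = 32 to 42 (11 days).

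| Sample day | Contaminating infusion days | Earlier use only: contaminated, not triggered | Earlier use only: clean, triggered | Literal: contaminated, not triggered | Literal: clean, triggered |
|---|---|---|---|---|---|
| 40 | 31–40 | 31 | 41–42 | 31 | 41–52 |
| 42 | 33–42 | none | 32 | none | 32, 43–52 |
| 44 | 35–44 | 43–44 | 32–34 | none | 32–34, 45–52 |

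**Literal reading, sample on Day 42.** Ten trigger days (43–52) fall after the sample. Week 8 is contaminated for *u* from 56 − 9 = 47 onward. So infusions on Days 43–46 (4 days) lead to Week 8, and those on Days 47–52 (6 days) lead to Week 10.

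**Earlier use only.** The mismatch remains, because the anchor is Day 42 and not the sample.

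**Week 7.** Day 49 is contaminated for *u* = 40 to 49. Of the 10 days that contaminate a Day 42 sample (33–42), Week 7 is clean for 33–39, which is 7, and still contaminated for 40–42, which is 3.

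**Same day.** The 10-day rule counts the whole day of use, so *s* − *u* = 0 is contaminated even when the infusion follows the sample. Protocol 6.2.2.3 arranges exactly that order for subjects on prophylaxis. Exempting it would reduce the contaminating days for a Day 42 sample from 10 to 9 (33–41).

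**From the 2.5-year cut.** Ten days equals 5 half-lives only if the half-life is 10 × 24 / 5 = 48 hours. For any other product half-life, the 10 days left in the fallback and the rule then in force give different answers.

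**The case against.** The strongest reply is that this is loose wording. The follow-on condition speaks of activity being still contaminated, which makes the first step a contamination test, and the rule spelled out later in the section looks forward only. A reader might infer that the SAP prescribes a window on both sides of Week 6. It does not say so, and the context points to use before the sample. That stands, but it does not remove the anchoring problem in the earlier-use columns above.

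Protocol 6.2.2.3 also provides for visits to be moved, within the window, away from on-demand use. That makes the Day 40 / Day 31 case less likely. It does not help a sample already at Day 44. It can also create the opposite error: after an infusion on Day 33, a visit moved to Day 44 is 11 days clear, yet Day 33 is 9 days before Day 42, so the fallback discards the sample.

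A two-week step can be defended. Allowing for both windows, 14 − 2 − 2 = 10 days, so a single infusion up to the Week 6 sample has always cleared by Week 8. But a rule that takes the first clean weekly sample still reaches Week 8 when Week 7 is contaminated, so it is never later.

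Finally, SAP 6.7.1 describes the Week 6 and Week 52 cuts in the past tense, and SAP 6.1 says the 12-month report followed SAP version 1.0. A change now cannot alter the interim timing or the dose recommendation. All values are listed with a contamination flag, so a clean Week 6 value stays visible. Both points stand and limit the consequence.

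**Conclusion.** The point holds as an inconsistency in how the primary value is derived. On either reading, the fallback and the contamination rule can classify the same sample differently, and the fallback skips a scheduled sample that is often clean. It also keeps 10 days after the contamination rule has changed, although SAP 6.7.1 and 6.9 carry these analyses to 2.5 years and Month 60.

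The size is bounded. Each case affects one of three planned subjects, but the documents do not say how often an infusion falls in the relevant days. The 10 of 21 trigger days that follow a Day 42 sample are a calendar count and not a probability. A reader might infer that a reported Week 6 value, or the Phase 3 dose recommendation, was wrong. Nothing in the documents shows that any subject had an infusion in these days.

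The counts assume a single infusion, the 10-day rule in whole calendar days, and later visits on their nominal days.

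**What to change.** Replace the fallback sentence in SAP 6.7.1 with: *If the Week 6 sample is contaminated under the contamination rule in force for that data cut, applied to the actual sample date and time relative to preceding infusions (an infusion started after the sample, including on the same day, does not count), the first later scheduled sample that is uncontaminated is used (Week 7, then Week 8, and so on).*

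For the Week 6 and Week 52 cuts already run, document which sample supplied each subject's primary value and whether the revised rule would change it. Record the fallback in SAP Section 7 as well, since the protocol has none and that section lists only the change of contamination rule.

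The cost is one sentence, a small change to the derivation code and a short note on three planned subjects. No visits or samples are added, because weekly central samples to Week 12 are already scheduled. The downside is a change to the primary derivation after those cuts, which is why it should be documented openly.

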6.7.2 Secondary Efficacy Endpoints

FIX activity over 52 weeks (and 2.5 years) (post IMP administration), annualized FIX consumption, Prophylaxis FIX replacement therapy use over 52 weeks (and 2.5 years), and on-demand FIX replacement therapy use over 52 weeks (and 2.5 years) will be presented using descriptive statistics across subjects for each visit and across time for each subject.

Bleeding episodes and annualized bleeding rates in the post-prophylaxis period and type (spontaneous bleeds, joint bleeds, and traumatic bleeds) will also be presented using descriptive statistics. All events that are emergent during the period will be counted.

The end of continuous prophylaxis requires 3 events: (1) study drug was administered, (2) uncontaminated factor IX activity (post-study drug) has since been observed to be $\geq 5\%$, and (3) the subject has not used exogenous factor IX for some contiguous time period of at least 15 days after study drug administration. The tenth day of the first 15-day contiguous period where these criteria are met is then taken as the end of prophylaxis. The Post-Continuous-Prophylaxis period begins on the day after the end of continuous prophylaxis. If the field for whether the bleed was treated is missing, then (for conservativeness) it will be assumed that the bleed was treated with factor IX. If the assessment field for newness of the bleed is missing, then (for conservativeness) it will be assumed that the bleed is new. If the assessment field for trueness of the bleed is missing, then (for conservativeness) it will be assumed that the bleed is true. A supplemental analysis will count only bleeds that were treated with exogenous factor IX. A supplemental analysis will count only bleeds that are assessed by the investigator to be new and true bleeds (per entry on the CRF).

[figure not shown]
In the analysis (from the 2.5-year data cut henceforth), any person-time during the post-treatment period within 5 half-lives subsequent to exogenous factor IX use will not be counted in the time at risk of (having) a bleeding event. Both the date and time of the exogenous factor IX injection start will be taken into account to identify time periods to be excluded. Nevertheless, any bleeds occurring during the post-prophylaxis period should still be counted as events, even if they

occurred during a time interval of “contamination”. See further detail in the [Data Handling Rules Appendix](#) in this document [under the category of “Contamination due to exogenous factor IX (infusion) use”].

Per subject plots of FIX activity levels over time, and per-subject plots of FIX replacement therapy use over time will be presented.

A plot of the cumulative number of bleeding episodes by type (spontaneous, traumatic, and joint bleeding events) over intervals of time will also be provided.

All data will also be listed.

6.8 Safety Analyses

6.8.1 Adverse Events

The version of the Medical Dictionary for Regulatory Activities (MedDRA) that is current at the time of database lock will be used to code verbatim terms for AEs for final analysis of the data. A glossary of MedDRA preferred terms used for adverse events reported in the study along with the associated Investigator's verbatim term will be provided.

An adverse event is considered on-treatment (i.e. treatment-emergent) if an event occurs after the dose of study drug, or if the AE worsened during the study after the dose of IMP (intensity and/or severity changed to a worsened grade). An adverse event that begins on the same date as the dose of study drug is treatment-emergent if the AE begins after the time of dose or if the time of AE onset is unknown. Adverse events are collected from the time informed consent is signed.

All treatment-emergent AEs are tabulated by SOC and preferred terms within each SOC according to the MedDRA terminology list. TEAEs will also be tabulated by severity (mild/moderate/severe using the Common Terminology Criterion for Adverse Events severity grades) and by relationship (related/not related) to trial medication, using frequency counts (number of subjects with event and number of events) and percentages. Similar tables will be created for TEAEs leading to premature treatment discontinuation (i.e. for which the infusion of study drug was stopped mid-infusion), deaths, and SAEs.

These summary tables will be presented by decreasing frequency of occurrence based on SOC and Preferred Term.

An AE overview table will be created displaying the number of subjects (and percentage) experiencing an event and the number of events for: Any TEAE, Mild/moderate/Severe TEAE, Related/Unrelated TEAE, Serious TEAE, and TEAEs leading to discontinuation (i.e. for which the infusion of study drug was stopped mid-infusion).

The summary tables will be accompanied by individual subject listings of all AEs, including information on AE number, actual AE description, date/time of start and end of AE, preferred term (MedDRA), SOC (MedDRA), severity, relationship/causality, type of AE, seriousness and outcome. Pre-existing AEs will be flagged. Pre-existing AEs are not considered to be treatment-emergent, except in case of worsening during/after trial treatment (to be collected as separate AE). Separate listings will be created for SAEs and deaths. AEs qualifying for special notification will also be tabulated for those types that can be identified programmatically. The categories of AEs qualifying for special notification are tabulated below.

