4.5.1 Reasons for Discontinuation

The reasons for discontinuation from this gene therapy trial include:

- AE
- Withdrawal by principal Investigator
- Withdrawal by subject
- Lost to follow-up

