5.3 Dosing and Administration

AMT-061 will be administered at a dose of 2×10^{13} gc/kg as a one-time infusion in a peripheral vein. The subjects will be monitored for tolerance to the IMP and detection of immediate AEs for 24 hours (overnight stay) after dosing.

The dosing of the subjects must be separated by a minimum of 14 calendar days to allow for subject safety monitoring and to ensure appropriate action can be taken in case any acute reactions are observed.

Detailed instructions for IMP handling e.g., receipt, storage, preparation, administration, cleaning, destruction and the recording of these critical activities will be described in the IMP Handling Manual.

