9.10 Safety Analyses

All treatment-emergent AEs are tabulated by SOC and preferred terms within each SOC according to the MedDRA terminology list. TEAEs will also be tabulated by severity (mild/moderate/severe using the Common Terminology Criterion for Adverse Events severity

Version: 4.0 (Amendment 3.0)

grades) and by relationship (related/not related) to trial medication, using frequency counts (number of subjects with event and number of events) and percentages. Similar tables will be created for TEAEs leading to premature discontinuation, deaths, and SAEs, if applicable.

These summary tables will be presented by decreasing frequency of occurrence based on SOC and Preferred Term.

An AE overview table will be created displaying the number of subjects (and percentage) experiencing an event and the number of events for: Any TEAE, mild/moderate/severe TEAE, related/unrelated TEAE, serious TEAE, TEAE for special notification, TEAE leading to discontinuation.

The summary tables will be accompanied by individual subject listings of all AEs, including information on AE number, actual AE description, date/time of start and end of AE, preferred term (MedDRA), SOC (MedDRA), severity, relationship/causality, type of AE, seriousness and outcome. Pre-existing AEs will be flagged. Pre-existing AEs are not considered to be treatment-emergent, except in case of worsening during/after trial treatment (to be collected as separate AE). Separate listings will be created for TEAEs for special notification, deaths, and SAEs, if applicable.

Summary statistics for the baseline assessment and change from baseline at each post-baseline visit for scheduled lab assessments of continuous laboratory variables will be tabulated. Clinically significant laboratory values will be tabulated. Clinical laboratory tests will be listed and summarized by visit, with reference range and flag indicating if the measurement in question is outside the reference range provided.

Summary statistics of the absolute value and change from baseline for vital sign measurements will be tabulated by visit, and time point. Vital sign measurements will be listed.

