Subjects With at Least One TEAE[a]	xx (xx.x) [xxx]
Mild TEAE	xx (xx.x) [xxx]
Moderate TEAE	xx (xx.x) [xxx]
Severe TEAE	xx (xx.x) [xxx]
Subjects With TEAEs Related to Study Treatment [b]	xx (xx.x) [xxx]
Subjects With TEAEs Unrelated to Study Treatment [b]	xx (xx.x) [xxx]
Subjects With Serious TEAEs	xx (xx.x) [xxx]
Subjects With AEs of Special Notification	xx (xx.x) [xxx]
Subjects With TEAEs Leading to Premature Treatment Discontinuation	xx (xx.x) [xxx]
Deaths - All Causes	xx (xx.x)

[a] TEAE = Treatment-Emergent Adverse Event.
[b] Related = Possibly related or related.
MedDRA Version xx.x was used for coding.

Source: Listing 4.4.1

Report generated by program: PPD

Version yyyy-mm-dd xx:xx

(Page n of N)

AMT-061 (AAV5-hFIXco-Padua)
 Trial ID: CT-AMT-061-01

Version 3.0
 16 Jun 2021
 Page 41 of 156

Table 3.1.2 Treatment-Emergent Adverse Events by MedDRA Primary System Organ Class and Preferred Term
 Analysis Set: All Subjects Treated

System Organ Class Preferred Term	All Subjects (N=x)
	n (%) [Events]
At Least One TEAE	xx (xx.x) [xx]
System Organ Class 1	xx (xx.x) [xx]
Preferred Term 1	xx (xx.x) [xx]
Preferred Term 2	xx (xx.x) [xx]
System Organ Class 2	xx (xx.x) [xx]
Preferred Term 1	xx (xx.x) [xx]
Preferred Term 2	xx (xx.x) [xx]
Etc....	

TEAE = Treatment-Emergent Adverse Event.
 MedDRA Version xx.x was used for coding.

Source: Listing 4.4.1

Report generated by program: PPD

Version yyyy-mm-dd xx:xx

(Page n of N)

Note to Programmer: Sort by decreasing frequency of occurrence based on system organ class. Within each system organ class, sort by decreasing frequency based on preferred term.

AMT-061 (AAV5-hFIXco-Padua)
Trial ID: CT-AMT-061-01

Version 3.0
16 Jun 2021
Page 42 of 156

Table 3.1.3 Serious Treatment-Emergent Adverse Events by MedDRA Primary System Organ Class and Preferred Term
Analysis Set: All Subjects Treated

TEAE = Treatment-Emergent Adverse Event.
MedDRA Version xx.x was used for coding.

Source: Listing 4.4.2

Note to Programmer: Similar to Table 3.1.2. Replace “At Least One TEAE” with “At Least One Serious TEAE”. Sort by decreasing frequency of occurrence based on system organ class. Within each system organ class, sort by decreasing frequency based on preferred term.

Table 3.1.4 Related Treatment-Emergent Adverse Events by MedDRA Primary System Organ Class and Preferred Term
Analysis Set: All Subjects Treated

TEAE = Treatment-Emergent Adverse Event.
MedDRA Version xx.x was used for coding.

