11. DATA REPORTS FOR REVIEW BY THE DMC

For each data review meeting, the DMC Data Reports will be provided to each DMC member by the DMC Secretary via a suitable secure method for their prior review. The report will be delivered approximately 10 business days before each DMC meeting.

The DMC Data Report for the DMC includes the tables, figures, and listings (TFLs) to be reviewed by the DMC members at the scheduled and/or ad hoc meetings. Mock-ups of the report format and content (i.e., TFL shells) are provided for CT-AMT-061-01 in [Appendix 4](#) and for CT-AMT-061-02 in [Appendix 5](#). The Sponsor and DMC members will review and approve the format and content of the mock-up DMC Data Report prior to the first DMC data review meeting.

The following descriptive summaries and listings will be included in the DMC Data Report based on the cumulative data in the study.

- Baseline demographic tables and results of the number of subjects screened, randomized or discontinued (with reasons for discontinuation) for the study
- List of frequent AEs (>5%) listed in order of frequency, from high to low and summarized of all SAEs and AEs leading to study discontinuation
- Summaries of all potentially clinically significant (PCS) laboratory results and vital signs
- Summaries of increases in alanine aminotransferase (ALT) and aspartate aminotransferase (AST)
- NAB titer
- Capsid-specific T-cells
- FIX activity levels

A subset of these outputs will be provided for DMC review after every set of approximately 10 subjects enrolled, for assessment of the impact of NABs. This subset of outputs will be identified in the DMC Data Report shells.

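### SAP 6.8.1 limits AE-related discontinuation to a stopped infusion, so an AE that later ends a subject's trial participation cannot enter the AE discontinuation row or tables

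*SAP*

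**What the plan says.** Protocol 9.10 states: "Similar tables will be created for TEAEs leading to premature discontinuation, deaths, and SAEs, if applicable". It also asks for a discontinuation line in the AE overview table. Neither item is restricted to the infusion. The protocol gives no formal definition of premature discontinuation, but its usage is consistent. Section 4.5.1 begins "The reasons for discontinuation from this gene therapy trial include" and puts AE first in the list. Section 6.1.3.1 sets out the assessments for a subject who discontinues before Week 52, or between Week 52 and Month 60.

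SAP 6.8.1 plans the corresponding tables for "TEAEs leading to premature treatment discontinuation (i.e. for which the infusion of study drug was stopped mid-infusion), deaths, and SAEs" and repeats the parenthetical definition for the overview table. In the Table 3.1.1 shell the only discontinuation row is "Subjects With TEAEs Leading to Premature Treatment Discontinuation", and no footnote gives the mid-infusion meaning. SAP 6.9 carries the same analyses forward to the Month 60 addendum. SAP Section 7, on changes from the protocol's methods, mentions only the factor IX contamination rule.

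AE-driven withdrawal is handled elsewhere too. SAP 6.4 plans summary tables of reasons for leaving the study and a disposition listing. Table 1.1 has a row for early withdrawal with Adverse Event among the reasons, but its programmer note shows a reason only when its count exceeds 1. Section 11 of the DMC charter, filed with the SAP, lists a report item "summarized of all SAEs and AEs leading to study discontinuation".

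**The concern.** Protocol 5.3 says "AMT-061 will be administered at a dose of 2×10^{13} gc/kg as a one-time infusion in a peripheral vein". Treatment can therefore be discontinued only while that infusion is running. A discontinuation category tied to treatment is closed to new events once the infusion ends, although follow-up lasts 60 months (Protocol 3.1).

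For a one-time, irreversible product, the informative question is whether any AE caused a subject to leave follow-up. The protocol uses this measure itself: its summary of the predecessor trial (1.3.2.2) reports that no AE led to discontinuation from that trial. Under the SAP wording, no AE summary table gives the matching statement for AMT-061. A reader of Table 3.1.1 also cannot see from the table how narrow the row is.

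**Working it through.** The plan states no figure for this point, so there is none to reproduce. The check sets the definitions side by side and follows one assumed case through the planned outputs.

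**Inputs**
- Planned number treated: 3 (Protocol 9.11; SAP 5.1). Protocol 9.12 allows up to three more, so at most 3 + 3 = 6 on that route.
- Treatment: one infusion (Protocol 5.3). Follow-up: 60 months (Protocol 3.1).
- SAP category: AEs for which the infusion was stopped before completion (SAP 6.8.1).
- Protocol category: AEs leading to premature discontinuation (9.10), read as leaving the trial from 4.5.1 and 6.1.3.1.

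**Assumed case.** One of the three treated subjects completes the infusion, later has an AE, and leaves the trial because of it.

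| Output | What it shows |
|---|---|
| Table 3.1.1 discontinuation row, SAP definition | 0/3 = 0.0% |
| Same row, trial-discontinuation meaning | 1/3 = 33.3% |
| SOC and preferred-term table of discontinuation TEAEs (SAP 6.8.1) | Event absent |
| General TEAE tables | Event counted |
| Table 1.1, early withdrawal row | Count of 1 |
| Table 1.1, Adverse Event reason line | Hidden, because 1 is not greater than 1 |

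With two or three such subjects the trial-discontinuation row would show 2/3 = 66.7% or 3/3 = 100.0%, and the SAP row would still show 0.0%. With one such subject among six it would be 1/6 = 16.7% against 0.0%.

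**Shells.** Tables 3.1.1 to 3.1.9 include no SOC and preferred-term shell for discontinuation TEAEs, although SAP 6.8.1 promises such a table. The disposition and demographics group in the list of shells contains only Tables 1.1 and 1.2, so Table 1.1 appears to be the shell that carries the withdrawal reasons promised in SAP 6.4.

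**Link from exit to event.** The AE listing fields named in SAP 6.8.1 include no item for an AE that led to withdrawal. That list need not be complete, and the listing shells are not in the public file, so it cannot be said that the final listing lacks the item.

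**The case against.** The strongest reply is that nothing is lost. The event stays in the TEAE, severity and relationship tables and in the listing of all AEs. The exit appears in the early withdrawal row, in the withdrawal-reason summaries and disposition listing of SAP 6.4, and in the DMC report. The Table 3.1.1 row says Treatment in its label, so it does not claim that no AE led to leaving the trial. Protocol 9.10 does not say what is being discontinued, and it qualifies its tables as applicable only where relevant. With three subjects, individual listings and no inference, no decision threshold depends on this row.

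Most of this stands, and it sets the limits of the point. A reader might infer that an AE-driven exit would be reported as zero throughout, or that the disposition outputs offer no backup. The documents do not support either reading: the zero is confined to the AE discontinuation row and tables, and the Table 1.1 note governs Table 1.1 alone. A reader might also infer that the SAP narrows Protocol 4.5.1 and the DMC charter. It does not. Section 4.5.1 lists reasons and plans no analysis, and the charter is a separate deliverable with its own shells.

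What the reply does not remove is an undeclared difference from the protocol's usage, no AE summary of events that led to leaving the trial, and a display rule that hides the likeliest non-zero count when three subjects are treated.

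**Conclusion.** The point holds as a reporting gap. SAP 6.8.1 states a rule under which any AE arising after the infusion contributes zero to the AE discontinuation category for the rest of the 60 months, and Section 7 does not list this as a change from the protocol. In the assumed single case the row reads 0/3 (0.0%) where the trial-discontinuation meaning gives 1/3 (33.3%). That percentage only illustrates what one subject is worth at this sample size; it does not estimate how likely such an exit is.

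The conclusion rests on two things. First, premature discontinuation in Protocol 9.10 is taken to mean leaving the trial; this is an inference from 4.5.1 and 6.1.3.1, since the term is not formally defined. Second, the current SAP text governs the 2.5-year and Month 60 reports. SAP 6.1 says that the 12-month report followed SAP version 1.0, which is not available here, so nothing is concluded about that report. No efficacy endpoint is affected.

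**What to change.** - Keep the mid-infusion row in Table 3.1.1 and state its definition in a footnote.
- Add an overview row for TEAEs leading to discontinuation from the trial, with a supporting SOC and preferred-term table or, with three subjects, a flag in the AE listing.
- Change the programmer note to Table 1.1 so that a withdrawal reason with a count of 1 is shown.
- Record in SAP Section 7 how each discontinuation category is defined and how it relates to Protocol 9.10.

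The cost is one row, a footnote, a table or flag, a corrected shell note and a sentence or two of text. Protocol 4.5 already requires the withdrawal date, and the reason if given, on the eCRF. The documents do not show that the form identifies the specific AE behind a withdrawal, so a manual link may be needed, which is a small task for three subjects.
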